STUDY PROTOCOL PLAN AND STATISTICAL ANALYSIS PLAN (SAP)

UNIVERSITY CEU CARDENAL HERRERA

Principal investigator: [name] [name]

TITLE: Ultrasound Probe Pressure on the Intratendon Doppler Signal in Patellar Tendinopathy

Research and Ethics Committee of CEU Cardenal Herrera University Number: CEI20/073

NCT ID:

DATE: 12-09-2020

STUDY PROTOCOL PLAN

Objectives:

The objectives of our study have been the following:

- Analyze the influence of the pressure exerted on the probe on the variables of area, number of signals, pixel intensity, perimeter, solidity, perfusion index, circularity, major and minor diameter of the intratendon Doppler signal in the evaluation of patellar tendinopathy.
- To study the relationship between the pressure exerted on the probe and intratendon perfusion in the Doppler evaluation of patellar tendinopathy.

Volunteers who want to participate in the study will read the general information of the study and sign the informed consent to participate in the study.

Once the informed consent has been read and delivered, the evaluator will check that they meet the inclusion criteria.

A quasi-experimental study of a single group will be carried out, consisting of subjects with patellar tendinopathy with intratendon hyper vascularization. Intratendon vascularization will be quantified using a proprietary methodology using ImageJ 1.47v image analysis software, determining the different variables related to the Doppler signal within an intratendon region of interest.

The first contact with the patient likely to participate in the project will always be made by the same researcher who will duly inform them of the study and provide informed consent in case of accepting participation for the performance of the exploratory ultrasound. Subsequently, a general questionnaire will be completed, where sociodemographic data and other data referring to the injury and sports practice are collected, also adding the VISA-P questionnaire that assesses the symptomatic severity, the severity of the symptoms and the capacity functional function in patients with patellar tendinopathy. Lastly, the ultrasound examination will be carried out in power-Doppler mode.

The ultrasound examination will begin with the positioning of the patient on the table in

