the supine position and with both knees extended. At the level of the knee to be explored, a support with an articulated arm will be placed where the probe attached to the force meter will be fixed. After positioning the articulated arm, a power-Doppler ultrasound scan of the intratendon vascularization will be carried out, making longitudinal cuts of the patellar tendon and using previously pre-established Doppler optimization parameters for all patients. The optimization parameters of the power-Doppler signal will be set at a Doppler frequency of 6.7 MHz, pulse repetition frequency (PRF) of 0.7 kHz. The lowest wall filter and a standardized gain just below the level that produces random noise will be applied.

This examination will be repeated several times with different probe pressures, which will be quantitatively adjusted through the force sensor and maintained with the articulated arm. A 4-second static video will be recorded of the longitudinal section that presents a higher Doppler signal in each of the scans at different probe pressures.

These videos will be saved for later analysis with ImageJ 1.47v software (Wayne Rasband, National Institutes of Health, USA, 2012) to determine and quantify the presence of intratendon Doppler signal.

The processing and analysis of the videos and images will be carried out on the image with the highest and lowest Doppler signal of each stored video. Once the image has been scaled, a region of interest (ROI) with dimensions capable of encompassing the intratendon Doppler signal will be selected individually.

To quantify the Doppler signal, the saved image with the highest Doppler signal of each video was selected and the area of color pixels was calculated.

To quantify the flux, the pixel color mean of the Doppler signals of each image was calculated. The mean pixel color of the image with the highest signal was considered as data of the maximum systolic velocity, and the one with the lowest signal as the final diastolic velocity. These data were transferred to the IR formula, obtaining a value associated with the intratendinous flow pattern (perfusion index).

In the images that did not detect a Doppler signal, or did not present an intratendon Doppler signal in diastole, the IR was determined as 1, which represents normality in the musculoskeletal tissue.

In addition, the parameters of number of signals, mean intensity of the pixel, area,

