perimeter, major and minor diameter, circularity and solidity were automatically calculated on the selected images with the highest Doppler signal of each recording.

This methodology will be carried out following the previously established and standardized order, based on standardized protocols for both subject positioning and echo-Doppler exploration. The ultrasound examination and subsequent analysis of the images will be described exactly and precisely so that they can be easily reproducible. All data obtained will be recorded in a computer spreadsheet to make the final statistical analysis easier and to obtain a greater and faster interpretation of the results.

Statistical Analysis Plan (SAP)

First, all the variables of interest will be detected and later they will be coded, labeled and transferred to a database. A data collection notebook (CDN) will be created where the variables, their reference values, measurement system and interpretation will be described and which will be available to all members of the working group. The programs used will be Microsoft © Access and Excel for initial data registration and IBM SPSS Statistics 19.0 for analysis.

Data debugging and control systems

The data related to the clinical information of the subjects and related to the questionnaires will be recorded in a database created for this purpose (Microsoft Access ©) with data entry protection systems. The same researcher will always record the data and a feedback review will be carried out for the detection of errors and lost cases by a third person. Missing and out-of-range screening will be performed.

The data related to the variables obtained by image analysis of ultrasounds will be exported in an automated way with a macro created for this purpose from the data analysis program in ASCII format to avoid incompatibilities between the image analysis program and the imaging programs. statistical analysis.

Exploratory Data Analysis (EDA)

Qualitative variables will be summarized in the form of counts and relative frequencies and, where appropriate, absolute frequencies and their confidence intervals (95% CI). Graphic summaries will be made using bar diagrams.

The quantitative variables will be summarized by means, standard deviations, medians, and interquartile ranges. Confidence intervals will also be provided for each of the measures. Graphical summaries will be made using box plots and bar diagrams with 95% CI.

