A univariate analysis of outliers will be carried out and their influence will be verified through the Z scores. Multivariate analysis of atypical cases and their influence will be carried out using the Mahalanobis distance.

Unusual cases will be removed from the analysis only if it is certain that they are wrong.

It will be checked whether the quantitative variables of interest follow a normal distribution (Kolmogorov-Smirnov test). The normality tests will be accompanied by the Q-Q normality graphs with and without trend that will aid interpretation and decision-making. In the event that any of the variables of interest does not conform to a normal distribution, a transformation of this will be carried out until it is achieved as long as its interpretation is not compromised.

Analysis of data

In the case of fulfilling the assumption of normality, parametric tests will be chosen and if not, the non-parametric alternatives will be chosen.

The measurement pattern used will be randomized, all subjects will be assigned to a minimum or a maximum probe pressure as the start of the measurements. The randomization factor (pressure) is included as a fixed effect, which will prevent a possible

interaction between pressure and the quantification of the Doppler signal.

To perform the statistical analysis, in the case that the variables present normality, the Pearson correlation coefficient will be used for quantitative variables. In order to better visualize the joint behaviour of both variables, scatter diagrams will be added and to determine the effect size and interpret the degree of shared variance, the coefficient of determination will be calculated. In the event that any variable does not present normality, the Spearman Rho correlation test will be chosen.

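### No rule for circularity, solidity or signal-pixel intensity in empty frames: a pooled correlation with pressure could absorb signal loss, so analyse them within subject

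*Combined protocol and SAP*

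**What the plan says.** The Objectives name nine Doppler variables to be related to probe pressure, among them pixel intensity, circularity and solidity. The design paragraph describes one group "consisting of subjects with patellar tendinopathy with intratendon hyper vascularization", and each subject is scanned repeatedly at different pressures.

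The image-processing paragraphs contain one rule for absent signal, and it assigns a value to a single variable: "the IR was determined as 1, which represents normality in the musculoskeletal tissue". It applies both to images with no signal at all and to those lacking it only in diastole. The remaining parameters come from a single frame per recording: "circularity and solidity were automatically calculated on the selected images with the highest Doppler signal of each recording". No condition is attached that this frame must contain signal. The same section promises that "The ultrasound examination and subsequent analysis of the images will be described exactly and precisely so that they can be easily reproducible".

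In the SAP under Data debugging and control systems, "Missing and out-of-range screening will be performed" closes the paragraph on clinical and questionnaire data. The image-data paragraph says only that results are "exported in an automated way with a macro created for this purpose". Under Analysis of data, "the Pearson correlation coefficient will be used for quantitative variables" if normality holds, with Spearman's rho otherwise. Pressure is also called a fixed effect there, but no model, outcome or subject term is named.

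**The concern.** Circularity and solidity describe a detected region. If the best frame of a recording shows no signal, there is no region to describe. The plan saw this for the IR and left it open for the shape variables. Two analysts following the text could write 0 or drop the frame, and report different coefficients from the same images.

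The choice matters because signal is likely to be lost more often as pressure rises, and pressure is the study's exposure. If frames from all subjects enter one correlation, zeros cluster at high pressure and produce a negative coefficient even when shape does not change. If empty frames are dropped, the subjects left at high pressure are the more vascular ones, which biases the coefficient for any variable that goes with vascularity. In both cases a coefficient labelled shape or intensity is partly a result about signal survival.

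**Working it through.** **Step 1. Which variables lack a value in an empty best frame?**

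- IR: set to 1 by the plan.
- Area and number of signals: naturally 0.
- Perimeter and the two diameters: no rule, but 0 is a natural convention.
- Circularity and solidity: no value.
- Mean intensity: depends on the averaging region. The flux paragraph averages over Doppler signals, which gives no value. The design paragraph speaks of variables within a region of interest (ROI), which would give one. The text does not settle this.

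Signal missing only in the lowest-signal frame does not create the gap, because these variables use the highest-signal frame.

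**Step 2. Does other text close it?** Screening detects missing values but does not say how to treat them. The exploratory-analysis rule deletes an outlier only when it is known to be an error, and a true empty frame is not an error. The planned data notebook or the export macro may hold a rule, but none is stated.

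**Step 3. How large could it be?** The documents give no sample size, pressure levels, loss rate or SDs, so there is no figure to reproduce. The following is a simulation with every input assumed: 20 tendons, 5 pressures, 4,000 replicates for dropping and 1,500 for zeros.

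- Signal = vascularity (SD 1) - b x pressure step + image noise (SD 0.5), lost below a limit 1.5 SD under mean vascularity. Only tendons with signal at the lowest pressure enter; b is set to give the stated loss at the highest.
- Variable = tendon value (SD 1, correlation c with vascularity) - 0.20 x step + noise (SD 0.5). For the zero rows the true effect is 0, the mean lies 4 SDs above 0, and c = 0.

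| Loss at highest pressure | 9% | 15% | 26% | 40% | 53% |
|---|---|---|---|---|---|
| Zeros, no effect: Pearson | -0.08 | -0.13 | -0.21 | -0.30 | -0.38 |
| Zeros, no effect: Spearman | -0.05 | -0.09 | -0.16 | -0.24 | -0.33 |
| Dropped, pooled slope, c = 0 | -0.20 | -0.20 | -0.20 | -0.20 | -0.20 |
| Dropped, pooled slope, c = 0.4 | -0.19 | -0.18 | -0.17 | -0.15 | -0.14 |
| Dropped, pooled slope, c = 0.8 | -0.18 | -0.16 | -0.14 | -0.11 | -0.075 |
| Within-tendon slope, independent error | -0.20 | -0.20 | -0.20 | -0.20 | -0.20 |
| Within-tendon slope, error shared with detection (0.8) | -0.19 | -0.19 | -0.17 | -0.16 | -0.15 |

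On the SAP's own scale, the coefficient of determination, zeros alone give 0.13² = 0.017 at 15% loss and 0.30² = 0.09 at 40%. For dropping at c = 0.4, pooled r is about -0.24 against -0.26 with complete data at 15% loss (r² 0.058 against 0.068), and -0.20 against -0.26 at 40% (0.040 against 0.068).

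**Step 4. Sensitivity.** With the mean 2 to 6 SDs above 0 and c of 0 or 0.8, zero-filled Pearson runs from about -0.06 to -0.15 at 15% loss and from -0.17 to -0.33 at 40%. Over 10 to 40 tendons at 5 levels, and 20 tendons at 3 or 8 levels, the share of the slope kept after dropping at c = 0.8 is 0.80-0.82 at 15% loss and 0.51-0.54 at 40%.

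A second simulation used different assumptions: 30 subjects, 5 pressures, circularity mean 0.60 and SD 0.15, no true effect, and loss rising from 1% to 10/20/40/60%.

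- Zeros, c = 0: Pearson -0.10/-0.18/-0.32/-0.44, significant at an assumed two-sided 5% in 14/63/99/100% of datasets.
- Dropped: about 0 at c = 0, +0.02/+0.05/+0.08/+0.11 at c = 0.5, and +0.04/+0.07/+0.13/+0.19 at c = 0.8.
- Within-subject correlation on frames with signal: between -0.004 and 0.004 throughout.

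**The case against.** The best case for the plan has five parts.

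1. Enrolment requires hypervascularization, so empty best frames may be rare, at least at low pressure. This stands. The loss rate is unknown, and the heavy-loss columns have no support in the documents.
2. A reader might infer that dropped frames vanish without trace. They do not: the same frame would normally carry area 0, signal count 0 and IR = 1, and scatter diagrams for the shape variables would show fewer points. Signal loss is therefore already partly captured by planned outcomes. What is missing is a tabulation by pressure.
3. A reader might take all three variables as undefined. That is firm only for circularity and solidity; for intensity it depends on the averaging region.
4. For those two shape variables the harm is least certain. Dropping causes no bias if shape is unrelated to signal survival, and nothing in the documents says that the macro writes 0. This stands as a limit on size, but the text rules out neither route.
5. Pooling is inferred, and a subject term would be needed for repeated measurements anyway. This is true, and it is why the within-subject analysis is the main fix and the coding rule a supporting one. Zeros and dropped frames still yield different datasets under any analysis.

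The planned Q-Q plots, transformations and outlier checks would probably reveal a spike of zeros. They do not say what to do with it.

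**Conclusion.** The gap is real but bounded. The plan gives no empty-frame value for circularity and solidity, nor for mean intensity if it is averaged over signal pixels. The only named test carries no subject term, although each subject contributes several pressures. If the correlation is pooled, zeros make it partly a measure of signal loss. Dropping weakens or distorts it when the variable tracks vascularity, and is harmless when it does not.

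The size cannot be computed from the documents. Under the stated assumptions the distortion is small up to about 15% loss at the highest pressure and material above about 40%. Small refers to the size of the coefficient: with zeros and 30 subjects, false significance is already common at 20% loss. In a separate run at 40% loss and c = 0.8, dropping cut the pooled slope from -0.20 to about -0.10, detected at the 5% level in 21% of datasets. The within-tendon slope stayed at -0.20 and was detected in 99%.

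A reader might go further and conclude that the planned analysis is biased. The documents do not support that: they state neither the pooling, nor the handling of empty frames, nor how often such frames occur.

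**What to change.** **Main change (SAP, Analysis of data).** Relate circularity, solidity and mean intensity to pressure within subject, by a mixed model with a subject effect or by per-subject slopes, over frames with signal. Use this in place of a pooled Pearson or Spearman correlation.

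**Supporting changes (SAP and data notebook).**
- Code circularity and solidity, and intensity if averaged over signal pixels, as missing and not 0 in empty frames.
- State whether intensity is averaged over signal pixels or over the ROI.
- Tabulate the number and percentage of tendons with signal at each pressure, from the area and count data already planned.

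**Cost.** SAP wording and a small change to the export macro; no new data. Conclusions on shape and intensity would apply only where signal persists. Some bias remains if image-level error affects both detection and the measured value: in the illustration, about -0.16 against -0.20 at 40% loss.

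### No confidence interval is planned for the within-tendon effect of probe pressure, and the descriptive single-variable intervals cannot stand in for one

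*Combined protocol and SAP*

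**What the plan says.** The Objectives section sets the first aim: "Analyze the influence of the pressure exerted on the probe on the variables of area, number of signals, pixel intensity", and further Doppler variables. The study protocol plan describes the design as follows: "A quasi-experimental study of a single group will be carried out". Of the scan it says: "This examination will be repeated several times with different probe pressures". Under Analysis of data, randomization decides only whether a subject starts at the minimum or the maximum pressure.

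Confidence intervals appear in one place, the SAP section Exploratory Data Analysis (EDA). They are planned for frequencies of qualitative variables and, after the list of summary statistics for quantitative variables, "Confidence intervals will also be provided for each of the measures". The section then adds: "Graphical summaries will be made using box plots and bar diagrams with 95% CI". It does not say whether the intervals or bars are produced separately by pressure.

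Under Analysis of data, if the variables are normal, "the Pearson correlation coefficient will be used for quantitative variables", with Spearman's rho otherwise. For effect size, "the coefficient of determination will be calculated". No interval is attached to either. The same section says that the randomized factor, identified as pressure, enters as a fixed effect, but it names no model, no subject term and no interval for the estimate.

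**The concern.** With one group and repeated scans, the quantity behind the first objective is how much a Doppler variable changes within a tendon as pressure changes. The plan followed as written never reports that change with its precision. The correlation and the coefficient of determination describe association on a unitless scale, have no planned interval, and have no term for scans that come from the same subject.

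The descriptive EDA intervals would then be the only precision shown in the report. A mean at one pressure carries the differences between tendons, and those differences largely cancel when a tendon is compared with itself. A reader with nothing else to go on may use the descriptive intervals to judge the pressure effect, a purpose for which they are not built.

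**Working it through.** **Inputs.** The documents give no sample size n, SD, number of pressures m or within-tendon correlation r, and no precision figure to reproduce. All values of these below are assumptions, shown over a range. One tendon per subject is assumed.

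**1. What is planned**

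| Quantity | Interval planned? |
|---|---|
| Frequencies of qualitative variables (EDA) | Yes |
| Summary measures of single quantitative variables, and bars (EDA) | Yes, grouping not stated |
| Pearson or Spearman correlation (Analysis of data) | No |
| Coefficient of determination (Analysis of data) | No |
| Fixed effect of pressure (Analysis of data) | No, and no model named |
| Within-tendon change or slope | Not planned |

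**2. If the bars are drawn by pressure.** Let s be the SD at each pressure.

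- SE of the mean at one pressure: s/√n.
- SE of a difference if two bars are read as independent: s√(2/n).
- SE of the within-tendon (paired) difference: s√(2(1−r)/n).
- Independent reading over paired: 1/√(1−r). Both n and s cancel.

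If the SD at one pressure is k times that at the other, the ratio becomes √[(1+k²)/(1+k²−2rk)].

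| Assumed r | Equal SDs | One SD halved (k = 0.5) |
|---|---|---|
| 0.2 | 1/√0.8 = 1.12 | √(1.25/1.05) = 1.09 |
| 0.5 | 1/√0.5 = 1.41 | √(1.25/0.75) = 1.29 |
| 0.8 | 1/√0.2 = 2.24 | √(1.25/0.45) = 1.67 |

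**3. One bar against the paired interval.** With equal SDs, the width of the paired-difference CI relative to a single bar is √(2(1−r)): 1.26 at r = 0.2, 1.00 at 0.5 and 0.63 at 0.8. A single bar is therefore wider than the paired interval only when r exceeds 0.5. If the SD is halved at high pressure, the paired interval is 1.34 times as wide as the high-pressure bar even at r = 0.8.

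**4. Illustration.** Assume n = 20, SD 6 and means 10 and 7, with t(19) = 2.093.

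- Bars: half-width 2.093 × 6/√20 = 2.8, giving 7.2 to 12.8 and 4.2 to 9.8, which overlap.
- Read as independent: SE 6√(2/20) = 1.90, t = 3/1.90 = 1.58, p = 0.12.
- Paired, r = 0.8: SE 6√(0.4/20) = 0.85, change 3.0 (95% CI 1.2 to 4.8), p = 0.002.
- Paired, r = 0.2: SE 6√(1.6/20) = 1.70, change 3.0 (95% CI −0.6 to 6.6).

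The same bars fit both paired results, so they cannot tell the reader which one holds.

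**5. If scans are pooled over m pressures as independent.** Ignoring any shift of the mean with pressure and taking the same r between all pressures, the naive SE of the overall mean is 1/√(1+(m−1)r) of the true SE.

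| m | r = 0.2 | r = 0.5 | r = 0.8 |
|---|---|---|---|
| 3 | 0.85 | 0.71 | 0.62 |
| 5 | 0.75 | 0.58 | 0.49 |

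Here the interval is too narrow for the mean it describes, and it is still not an interval for the pressure effect.

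**The case against.** The strongest case on the other side has four parts.

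- **The EDA section is generic description.** It covers all quantitative variables, and its bars are called graphical summaries. Inference sits under Analysis of data. Nothing says that overlap of bars will be used to judge the pressure effect. This stands.
- **A per-pressure CI is a correct interval for the mean at that pressure.** Between-tendon variance belongs in it. This also stands, and it is why those intervals need not be removed.
- **The size is unknown.** Each scan records the longitudinal section with the higher signal, so the plane may differ between pressures and lower r. The protocol also expects some images with no signal, so equal SDs cannot be presumed. This stands, and it is why low r and unequal SDs are shown above.
- **The SAP does mention a fixed effect for pressure.** That hints at a model. With no model, subject term or interval specified, it does not fill the gap.

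A reader might go further and infer that the plan's error bars at each pressure are too wide, or that they will lead to a false conclusion of no effect. The documents do not support either reading. They never say that the bars are drawn by pressure. They give no r, SD or n. The direction of the problem reverses if scans are pooled. Excess width arises only when bars are compared as independent and r is positive.

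**Conclusion.** The point holds as an omission. The plan studies a within-tendon effect and plans no confidence interval for it, and the descriptive intervals it does plan answer a different question under either grouping. This conclusion rests on the text alone and needs no assumed figure.

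The size is conditional. For bars drawn by pressure and compared as independent, the overstatement of the SE runs from about 1.1 to 2.2 over assumed r of 0.2 to 0.8 with equal SDs, and from 1.1 to 1.7 if one SD is half the other. A positive r is plausible because the same tendon is scanned repeatedly, but its size is not documented. For pooled scans, the naive SE is between 0.85 (m = 3, r = 0.2) and 0.49 (m = 5, r = 0.8) of the true one. The main gap lies in the Analysis of data section, and closing it is a cheap improvement worth making.

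**What to change.** In the Analysis of data section, add one of the following for each Doppler variable, and report it as the precision of the pressure effect:

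- the within-tendon change from the minimum pressure to each other pressure, with a 95% CI (paired t, or a bootstrap that resamples subjects for skewed variables); or
- the pressure effect with its 95% CI from a named model with a subject term, which would also make the existing fixed-effect sentence specific.

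In the EDA section, state how the intervals and bars are grouped and computed. Keep per-pressure means and CIs, labelled as descriptive. State that scans are not pooled over pressures as independent when any CI is computed.

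The cost is SAP wording and a little more analysis of data already collected. The change produces several intervals per variable across the nine Doppler variables named in the first objective. They should be presented as estimates, not as separate tests.

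### The SAP promises a fixed effect for the 'randomization factor (pressure)', but its only named association analyses, Pearson and Spearman, can hold neither that term nor a subject term

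*Combined protocol and SAP*

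**What the plan says.** The Study Protocol Plan describes one group in which each subject serves as their own comparison. On the power-Doppler scan it says: "This examination will be repeated several times with different probe pressures". The second objective is to study how probe pressure relates to intratendon perfusion.

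The SAP, under Analysis of data, makes four relevant statements:

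- On test choice in general: "parametric tests will be chosen and if not, the non-parametric alternatives will be chosen".
- On what is randomised: "all subjects will be assigned to a minimum or a maximum probe pressure as the start of the measurements".
- On adjustment: "The randomization factor (pressure) is included as a fixed effect, which will prevent a possible" "interaction between pressure and the quantification of the Doppler signal".
- On the analysis itself: "the Pearson correlation coefficient will be used for quantitative variables", with scatter plots, and "to determine the effect size and interpret the degree of shared variance, the coefficient of determination will be calculated". If a variable is not normal, "the Spearman Rho correlation test will be chosen".

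No regression, analysis of variance, mixed model, repeated-measures correlation, subject effect or sequence term is named anywhere. The Kolmogorov-Smirnov test, Z scores and Mahalanobis distance are named, but only as data checks.

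**The concern.** A fixed effect is a term in a model, and the SAP names no model that could contain it. A correlation coefficient relates two columns of numbers. It has no place for a starting sequence, a scan position or a subject. A reader is told that a term deals with a problem, yet the analysis described in the next paragraph cannot include that term.

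The same gap leaves the repeated scans unaddressed. The SAP does not say how several scans per subject enter one correlation. If every scan is treated as an independent row, the test uses the wrong error variance. It counts differences between subjects as noise although every subject is measured at each pressure, and it ignores that subjects may respond to pressure to different degrees.

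The wording of the adjustment sentence adds to the difficulty. It calls pressure the randomised factor, whereas only the start of the series is randomised. It also says the term will prevent an interaction between pressure and the Doppler quantification, and a main effect in a model cannot do that.

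**Working it through.** **Reading the text.** The plan gives no figure to reproduce, so the first step is to match each promise to a named analysis.

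| Element | Where stated | Can Pearson or Spearman carry it? |
|---|---|---|
| Several scans per subject | Study Protocol Plan, ultrasound examination | No, there is no subject term |
| Randomised start, minimum or maximum | SAP, Analysis of data | No, there is no sequence term |
| Fixed effect | SAP, Analysis of data | No, there is no model |

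**What pooling would do.** Everything here is assumed, because the documents give no sample size, number of levels, variance or drift. Take n = 20 subjects, 5 equally spaced pressures coded x = -2 to 2, and error SD 1. The model is Y = u + (b + g)·x + e, where u is the subject's level (SD σ), g is the subject's departure from the average slope (SD τ), and e is error.

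Per subject, the sum of x² is 10 and the mean of x² is 2. With b = 0:

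- The true variance of the pooled slope is (1 + 10τ²)/(10n).
- The variance the pooled test assumes is about (σ² + 1 + 2τ²)/(10n).
- Their ratio is q = (1 + 10τ²)/(σ² + 1 + 2τ²).
- The rejection rate at nominal 5% is about 2Φ(-1.96/√q).

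| σ | q, τ = 0 | Approx. | Simulated | q, τ = 0.30 | Approx. | Simulated |
|---|---|---|---|---|---|---|
| 0 | 1/1 = 1.00 | 5.0% | about 5% | 1.9/1.18 = 1.61 | 12.2% | about 12% |
| 0.5 | 1/1.25 = 0.80 | 2.8% | about 3% | 1.9/1.43 = 1.33 | 8.9% | about 9% |
| 1 | 1/2 = 0.50 | 0.6% | about 0.8% | 1.9/2.18 = 0.87 | 3.6% | about 4% |
| 2 | 1/5 = 0.20 | 0.001% | about 0.01% | 1.9/5.18 = 0.37 | 0.1% | about 0.3% |

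The simulated columns are for the pooled Pearson test with no drift. At τ = 0.50 and σ = 0 the simulated rate is about 20%.

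The ratio q exceeds 1, and the test over-rejects, when 10τ² > σ² + 2τ², that is, when 8τ² > σ². At τ = 0.30 the boundary is σ = √0.72 = 0.85. The documents give neither σ nor τ, so the direction of the error cannot be determined.

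**The within-subject alternative.** Because the x values sum to zero, the subject's level cancels from that subject's own slope. Averaging the per-subject slopes with equal weight over the two starting sequences gives rejection near 5% in every cell of the table.

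**Order.** Assume pressures run stepwise from the randomised start and an order effect of 0.3 per unit of x. If a fraction p start at minimum, the unadjusted average slope is biased by 0.3 × (2p - 1). That is 0 at p = 0.5, 0.06 at p = 0.6 and 0.12 at p = 0.7. Adjusting for sequence returns it to about 0. The SAP does not say whether starts are allocated in equal numbers.

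**The case against.** The strongest reply is that the plan does address order. It randomises the start, which is control by design, and it states an intended adjustment. The wording may simply be loose, with starting pressure meant throughout. Much of this stands. A reader might infer that the plan makes no provision for order, but the documents do not support that. The accurate statement is that the intended term sits in no named analysis. Randomising the start does protect the average slope against linear drift when starts are balanced and pressures run stepwise, although the stepwise order is an inference.

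A second reply is that pooling is nowhere stated. That is correct, and the error rates above are conditional on it. The gap itself does not depend on them, because the SAP gives no other way of using several scans per subject.

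A reader might also infer that pooled correlations are merely conservative, or that a within-subject model brings a general gain in power. Neither follows. Pooled Pearson is conservative when subjects share one slope but differ in level, and it can over-reject when slopes vary. At slope SD 0.30 and a true slope of -0.20, sequence-averaged per-subject slopes have about 49% power, no more than pooled Pearson at subject SD 1.

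Finally, r² falls as between-subject variance rises. That is part of its definition as shared variance and is not an error in the SAP. It does make r² a poor main summary of the pressure effect.

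**Conclusion.** The point holds as a gap in specification. The SAP states a fixed effect that its named analyses cannot contain, it names no analysis with a subject term for repeated scans, and it labels the exposure as the randomised factor. None of this rests on a numerical assumption, and it should be fixed before analysis.

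The consequence for error rates is conditional on pooling all scans and on assumed values. In the illustration, rejection under a true null ranges from about 0.01% to about 12% for slope SD 0 to 0.30, against a nominal 5%. The size and direction in this trial are unknown.

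A reader might take the clause about preventing an interaction to mean that the plan removes the very relationship it sets out to study. The text does not establish that. Order control is the more plausible intent, and the clause is best treated as ambiguous wording.

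**What to change.** 1. **Correct the sentence.** Replace it with: *The starting pressure (sequence: minimum-first or maximum-first) is randomised; pressure is the within-subject exposure of interest.* Delete the clause about preventing an interaction. Record the scan order for each subject, and state the order of pressures after the start and whether starts are allocated in equal numbers.
2. **Name the primary association analysis.** Use a repeated-measures mixed model with fixed effects for pressure, sequence and linear scan position, and a random subject intercept and pressure slope. If the random slope cannot be fitted, use per-subject slopes averaged with equal weight over the two sequences.
3. **Keep the existing transformation step first.** The Exploratory Data Analysis section already requires it. Only for outcomes that still fail normality, use a within-subject rank trend averaged over the two sequences.
4. **Change the main estimate.** Report the within-subject slope with its confidence interval. Keep Pearson, Spearman, r² and the scatter plots as descriptive.

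The cost is a little more analysis work, plus some power if subjects differ in neither level nor slope. At an assumed n = 20, 5 levels, error SD 1 and true slope -0.20, sequence-averaged per-subject slopes have about 74% power under simple randomisation or 76% with equal starts, against 80% for pooled Pearson.
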